1.5.2 Rationale for pembrolizumab dose selection

The planned fixed dose of pembrolizumab for this study in combination with cabozantinib is 200 mg IV every 3 weeks (Q3W). Based on the totality of data generated in the Keytruda development program, 200 mg Q3W is the appropriate dose of pembrolizumab for adults across all indications and regardless of tumor type.

As outlined below, this dose is justified by:

[figure not shown]
- Clinical data from 8 randomized studies in melanoma and NSCLC indications demonstrating flat dose- and exposure-efficacy relationships from 2 mg/kg Q3W to 10 mg/kg Q2W, representing an approximate 5- to 7.5-fold exposure range (refer to IB, Section 5.2.2)
- Population PK analysis showing that both fixed dosing and weight-based dosing provides similar control of PK variability with considerable overlap in the distributions of exposures, supporting suitability of 200 mg Q3W
- Clinical data showing meaningful improvement in benefit-risk including overall survival at 200 mg Q3W across multiple indications, and
- Pharmacology data showing full target saturation in both systemic circulation (inferred from pharmacokinetic [PK] data) and tumor (inferred from physiologically-based PK [PBPK] analysis) at 200 mg Q3W

Recently, the efficacy and safety of pembrolizumab 200 mg IV q3w in combination with the multikinase inhibitor lenvatinib has been evaluated in an investigational multicenter, multi-indication, open-label Phase 1b/1 clinical study³⁸ and a Phase 3 study is ongoing.

2.0 TRIAL DESIGN

This is a non-randomized Phase 2 trial using the Simon's optimal two-stage design. In the first stage, 13 eligible patients will enroll. If there are 2 or fewer patients with response (CR or PR), the study will be suspended for lack of sufficient efficacy. Otherwise, 16 additional patients will be accrued for a total of 29 patients. An accrual period of 24 months and follow-up period of 12 months are anticipated. More than 29 patients may be screened and/or enrolled depending on screen fails and dropouts before starting treatment.

Figure 2.1. Study schema

3.0 STUDY OBJECTIVES

3.1 Primary objectives

- To determine the objective response rate (ORR) of the combination of cabozantinib and pembrolizumab in the first-line treatment of advanced HCC based on RECISTv1.1.

3.2 Secondary objectives

- To assess the disease control rate (DCR) by RECIST v1.1, ORR and DCR by iRECIST, progression-free survival (PFS) by RECIST v1.1, and overall survival(OS).
- To assess the safety of the combination treatment with cabozantinib and pembrolizumab based on NCI CTCAE v5.

3.3 Exploratory objectives

- To explore the predictive biomarkers for cabozantinib and pembrolizumab in HCC using archival tissue or pre-treatment fresh tumor biopsy (if available) and pre-treatment peripheral blood.

4.0 STUDY ENDPOINTS

4.1 Primary endpoint

- Objective response (complete or partial response) per RECIST v1.1 (by blinded central review).

4.2 Secondary endpoints

- Objective response (complete or partial response) per iRECIST (blinded central review).
- Disease control (complete + partial response + stable disease) per RECIST v1.1 and iRECIST.
- Progression-free survival (PFS) is defined as time from study registration to radiographic progression per RECIST v1.1 (blinded central assessment), clinical progression, or death of anycause.
- Overall survival (OS) is defined as time from study registration to death of anycause.
- Safety will be evaluated by assessing AEs according to NCI CTCAE v5.

4.3 Exploratory endpoints

Exploratory biomarkers will be assessed using archival tumor tissue or pre-treatment fresh tumor biopsy (if available) and peripheral blood and correlated with tumor response. Tumor tissue will be assessed by multiplex immunohistochemistry (IHC) assay for intratumoral immune cell subsets and distribution, RNA sequencing (NanoString) for immune gene expression, and T cell receptor (TCR) clonality. The expression levels of biomarkers including c-MET, PD-L1 and PD-L2 in tumor cells and cells of the tumor microenvironment will also be assessed by IHC. Blood-based biomarkers will be explored, including circulating T cell subsets and cytokines.

5.0 SUBJECT SELECTION

To be eligible for the study, the subject must meet all of the inclusion criteria and none of the exclusion criteria.

5.1 Inclusion criteria

1. At least 18 years of age.
2. Must have a histologically confirmed diagnosis of HCC or a non-invasive diagnosis of HCC as per the American Association for the Study of Liver Diseases (AASLD) criteria.
 - c. If available, archival tissue must be submitted.
 - d. Mixed HCC-cholangiocarcinoma is not allowed.
3. Patient has BCLC stage C disease, or BCLC stage B disease that is not amenable to locoregional therapy or refractory to locoregional therapy, and not amenable to curative treatment.
 - a. Previous locoregional therapy is allowed (e.g. surgical resection, external beam radiation, catheter-based therapy), and patients must have evidence of disease progression from locoregional therapy.
4. Must have measurable disease by RECIST v1.1.
 - a. Lesions that were previously radiated or ablated cannot be target lesions unless there was subsequent radiographic progression at those sites.

RG1007034

5. No prior systemic therapy for HCC. Prior chemotherapy given locally into the liver (e.g. TACE) is allowed.
6. Must have Child-Pugh class A hepatic function within 7 days prior to first dose of study intervention (Appendix 6).
7. ECOG performance status 0-1 (Appendix 5).
8. Life expectancy of at least 12 weeks.
9. Recovery to baseline or \leq Grade 1 toxicities (CTCAE v5) related to any prior treatments, unless adverse events (AEs) are clinically nonsignificant and/or stable on supportive therapy.
10. Adequate organ and marrow function, based upon meeting all of the following laboratory criteria within 14 days before first dose of study treatment:
 - a. Absolute neutrophil count (ANC) $\geq 1500/\text{mm}^3$ without granulocyte colony-stimulating factor support.
 - b. Platelets $\geq 60,000/\text{mm}^3$ without transfusion within 14 days.
 - c. Hemoglobin $\geq 9 \text{ g/dL}$ ($\geq 90 \text{ g/L}$) without transfusion or EPO dependency within 14 days.
 - d. Alanine aminotransferase (ALT) and aspartate aminotransferase (AST) $\leq 5 \times$ upper limit of normal (ULN).
 - e. Total bilirubin $\leq 2 \text{ mg/dL}$ OR direct bilirubin $\leq \text{ULN}$ for participants with total bilirubin levels $>2 \text{ mg/dL}$.
 - f. Serum albumin $\geq 2.8 \text{ g/dL}$ ($\geq 28 \text{ g/L}$) without albumin infusion.
 - g. Prothrombin time (PT)/INR or partial thromboplastin time (PTT) test $\leq 1.5 \times \text{ULN}$.
 - h. Serum creatinine $\leq 1.5 \times \text{ULN}$ or calculated creatinine clearance $\geq 40 \text{ mL/min}$ using the Cockcroft-Gault equation (Appendix 7).
 - i. Urine protein/creatinine ratio (UPCR) $\leq 1 \text{ mg/mg}$ ($\leq 113.2 \text{ mg/mmol}$) or 24h urine protein $\leq 1\text{g}$.
 - j. Hemoglobin A1c (HbA1c) $\leq 8\%$ within 28 days before randomization or fasting serum glucose $\leq 160 \text{ mg/dL}$.
11. Patients with positive hepatitis B surface antigen (HBsAg) and/or HBV viral load $>100 \text{ IU/mL}$ at the time of enrollment are eligible to enroll on study if they meet the following criteria:
 - a. Anti-HBV therapy as per institutional practice must be given at least 4 weeks and HBV viral load must be $<100 \text{ IU/mL}$ prior to initiating study treatment. Patients on active HBV therapy with viral loads $<100 \text{ IU/mL}$ should remain on the same therapy throughout study treatment.
 - b. Note: Patients with positive anti-hepatitis B core antibody (HBcAb), negative HBsAg, and negative or positive anti-hepatitis B surface antibody, and who have an HBV viral load $<100 \text{ IU/mL}$ do not require anti-viral prophylaxis.
12. Patients with past or ongoing hepatitis C infection (HCV) are eligible to enroll on study, with or without prior anti-viral treatment, as long as the other eligibility criteria are met. Treated patients must have completed their anti-viral treatment at least 1 month prior to initiating study treatment.
13. Sexually active fertile subjects and their partners must agree to use effective methods of contraception (see Appendix 8) during the course of the study and for at least 4 months after the last dose cabozantinib. They must also refrain from donating sperm during this time period.
14. Female subjects of childbearing potential must not be pregnant at screening and not breastfeeding. Females of childbearing potential are defined as premenopausal females capable of becoming pregnant (i.e. females who have had any evidence of menses in the past 12 months, with the exception of those who had prior hysterectomy).
 - a. Women who have been amenorrheic for 12 or more months are still considered to be of childbearing potential if the amenorrhea is possibly due to prior chemotherapy, antiestrogens, low body weight, ovarian suppression or other reasons.
15. Capable of understanding and complying with the protocol requirements and must provide written informed consent/assent for the study.

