- h. Serum creatinine $\leq 1.5 \times$ ULN or calculated creatinine clearance ≥ 40 mL/min using the Cockcroft-Gault equation (Appendix 7).
- i. Urine protein/creatinine ratio (UPCR) ≤ 1 mg/mg (≤ 113.2 mg/mmol) or 24h urine protein ≤ 1 g.
- j. Hemoglobin A1c (HbA1c) $\leq 8\%$ within 28 days before randomization or fasting serum glucose ≤ 160 mg/dL.

11. Patients with positive hepatitis B surface antigen (HBsAg) and/or HBV viral load >100 IU/mL at the time of enrollment are eligible to enroll on study if they meet the following criteria:

- a. Anti-HBV therapy as per institutional practice must be given at least 4 weeks and HBV viral load must be <100 IU/mL prior to initiating study treatment. Patients on active HBV therapy with viral loads <100 IU/mL should remain on the same therapy throughout study treatment.
- b. Note: Patients with positive anti-hepatitis B core antibody (HBcAb), negative HBsAg, and negative or positive anti-hepatitis B surface antibody, and who have an HBV viral load <100 IU/mL do not require anti-viral prophylaxis.

12. Patients with past or ongoing hepatitis C infection (HCV) are eligible to enroll on study, with or without prior anti-viral treatment, as long as the other eligibility criteria are met. Treated patients must have completed their anti-viral treatment at least 1 month prior to initiating study treatment.

13. Sexually active fertile subjects and their partners must agree to use effective methods of contraception (see Appendix 8) during the course of the study and for at least 4 months after the last dose cabozantinib. They must also refrain from donating sperm during this time period.

14. Female subjects of childbearing potential must not be pregnant at screening and not breastfeeding. Females of childbearing potential are defined as premenopausal females capable of becoming pregnant (i.e. females who have had any evidence of menses in the past 12 months, with the exception of those who had prior hysterectomy).

- a. Women who have been amenorrheic for 12 or more months are still considered to be of childbearing potential if the amenorrhea is possibly due to prior chemotherapy, antiestrogens, low body weight, ovarian suppression or other reasons.

15. Capable of understanding and complying with the protocol requirements and must provide written informed consent/assent for the study.

Exclusion criteria

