7.3 Duration of therapy

Patients will begin cabozantinib and pembrolizumab concurrently. Patients may continue study therapy until unequivocal disease progression, unacceptable drug-related toxicity, or subject withdrawal. If one drug needs to be permanently discontinued due to toxicity, the other agent may be continued. Interval dosing interruption/delay of either or both agents is allowed for AEs (see Section 9.0).

Treatment beyond progression with cabozantinib and/or pembrolizumab (depending on patient tolerance) will be allowed based on meeting pre-specified criteria and after discussion with the study PI (see Section 12.1).

Patients may be treated up to a maximum of two years from the time of treatment initiation.

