9.3 Information on cabozantinib toxicity

AEs may occur within the first few weeks after starting cabozantinib (steady state reached at approximately 2 weeks). Cabozantinib-related AEs that generally have an early onset include hypocalcemia, hypokalemia, thrombocytopenia, hypertension, PPES, abdominal pain, mucosal inflammation, constipation, diarrhea, and vomiting.

AEs should be managed with supportive care at the earliest signs of toxicity. In all subjects, dose delays and reductions of cabozantinib to manage toxicity are allowed under the guidelines below. In general, grade 3 cabozantinib-related AEs require dose interruption until AEs recover to grade 1, at which point treatment may be resumed at the next lower dose. Moreover, dose reductions are recommended for

grade 2 events that, if persistent, could become serious and/or intolerable. **If cabozantinib is delayed by more than 4 weeks, it must be discontinued**, unless there is reason to believe that the patient will benefit from resuming cabozantinib. In this case, resuming cabozantinib at dose reduction must be discussed with the PI.

Furthermore, cabozantinib should be discontinued for the following AEs: visceral perforation or fistula formation, severe hemorrhage, serious arterial thromboembolic events, nephrotic syndrome, hypertensive emergency, persistent uncontrolled hypertension despite optimal medical management, and RPLS.

If an AE is believed to be probably/definitely related to cabozantinib, and not related to pembrolizumab, then pembrolizumab may be continued even if cabozantinib needs to be interrupted or discontinued, as long as pembrolizumab is not expected to delay recovery or worsen the AE.

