12.0 CRITERIA FOR TREATMENT DISCONTINUATION

Participants may discontinue study intervention at any time for any reason or be dropped from the study intervention at the discretion of the investigator should any untoward effect occur. In addition, a participant may be discontinued from study intervention by the investigator if study intervention is inappropriate, the study plan is violated, or for administrative and/or other safety reasons. Specific details regarding procedures to be performed at study intervention discontinuation are provided in Sections 11.4 and 11.5.

A patient will be discontinued from study treatment under the following circumstances:

- Progressive disease (PD) as per RECIST v1.1 or the subject no longer experiences clinical benefit as determined by the investigator (see Section 12.1 for criteria for continuing treatment beyond progression).
- Unacceptable toxicities despite supportive therapy and dose reduction/modification.

- Discontinuation of pembrolizumab for recurrent grade 2 pneumonitis.
- An AE or intercurrent illness/condition or personal circumstance which, in the opinion of the investigator, places the participant at unnecessary risk from continued administration of study intervention.
- Any progression or recurrence of another malignancy, or any occurrence of another malignancy that requires active treatment.
- Constraints of this protocol are detrimental to the patient's health.
- Necessity for treatment with other anticancer agents or other treatment prohibited by protocol.
- TRAE that results in interruption of cabozantinib > 4 weeks and pembrolizumab > 12 weeks, unless there is unequivocal evidence that the subject is benefitting. In this situation, a subject may be able to restart therapy upon resolution of the toxicity and with agreement of the Study PI.
- Patient requests discontinuation.
- Sexually active subjects who refuse to use medically accepted barrier methods of contraception (Appendix 8) during the course of the study and for 4 months after discontinuation of study treatment.
- Women who become pregnant or are breastfeeding.
- Request by regulatory agencies for termination of treatment of an individual subject or all subjects under the protocol.
- Significant noncompliance with the protocol schedule in the opinion of the investigator.

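### Inclusion 13 counts its 4-month contraception and sperm-donation tail from the last cabozantinib dose only, although pembrolizumab may continue alone and other sections count from the end of all treatment

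*Combined protocol and SAP*

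**What the plan says.** Inclusion 13 appears in the synopsis and in Section 5.1 with the same content. Sexually active fertile subjects and their partners must use effective contraception "during the course of the study and for at least 4 months after the last dose cabozantinib". The next sentence adds: "They must also refrain from donating sperm during this time period". No other rule on sperm donation is given in the protocol.

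The protocol plans for the two drugs to stop at different times. Section 7.3 states: "If one drug needs to be permanently discontinued due to toxicity, the other agent may be continued". Section 9.3 says of toxicity attributed to cabozantinib alone that "pembrolizumab may be continued even if cabozantinib needs to be interrupted or discontinued", provided that recovery is not expected to suffer.

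The other time windows use a different starting point:

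- Section 12.0 makes refusal of contraception a reason to stop treatment, and its window runs "for 4 months after discontinuation of study treatment".
- Sections 16.4.2 and 16.5.2 require pregnancies and lactation exposure to be reported for 120 days after study treatment ends, or 30 days if new anticancer therapy starts.
- Section 16.4.2 follows adverse events for 30 days after the final dose of either drug, whichever is later.

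**The concern.** The rule that each patient accepts at entry is tied to one of two study drugs, and the other may be the last one given. Inclusion 13 is the outlier: the other windows run from the end of all treatment. A patient who stops cabozantinib for toxicity and stays on pembrolizumab could meet the post-dose clause of inclusion 13 and still have less than the 4 months that Section 12.0 describes, or no tail at all. The matter at stake is reproductive safety in what is probably a small number of patients, and clear instructions to them. No estimate or test in the trial depends on it.

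**Working it through.** The plan gives no figure to reproduce here. The check is a comparison of dates.

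**Inputs.** The tail in inclusion 13 is 4 months from the last cabozantinib dose. The tail in Section 12.0 is 4 months from the end of study treatment. Both are taken as 120 days, using 30-day months. Let g be the number of months by which pembrolizumab outlasts cabozantinib. The documents give no value for g, so it is an assumption and is shown over a range.

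**Formula.** Days left by the post-dose clause after the last pembrolizumab dose = max(0, 120 − 30g).

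| g (months) | Inclusion 13, post-dose clause (days) | Section 12.0 (days) | Difference (days) |
|---|---|---|---|
| 0 | 120 | 120 | 0 |
| 1 | 90 | 120 | 30 |
| 2 | 60 | 120 | 60 |
| 3 | 30 | 120 | 90 |
| 4 or more | 0 | 120 | 120 |

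**Effect of the undefined phrase.** Inclusion 13 also applies during the course of the study, and the protocol does not say when that ends. For g of 4 or more there are three readings:

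- *It ends at the last dose.* No days remain, so the tail is 120 days short.
- *It ends at the treatment discontinuation visit, 30 (+7) days after the last dose.* 30 to 37 days remain, so the tail is 120 − 37 = 83 to 120 − 30 = 90 days short.
- *It ends with follow-up.* Treatment is capped at two years (Section 7.3). Under the 3-year limit in Table 10.1, footnote 20, at least 36 − 24 = 12 months remain and there is no gap. Under the 2-year limit in Sections 11.5 and 12.0, the full 4 months remain if the last dose is by month 24 − 4 = 20, falling to none for a last dose at month 24. This reading takes the study start date as the patient's own start.

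**Example.** Cabozantinib stops at month 2 and pembrolizumab at month 12, so g = 10. The post-dose clause ends at month 2 + 4 = 6. Cover after the last pembrolizumab dose is 0 months on the first reading, about 1 month on the second, and 4 months or more on the third. Section 12.0 runs to month 12 + 4 = 16.

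**Can g be large?** The protocol allows it. Section 9.3 lists events that end cabozantinib specifically, such as perforation, severe hemorrhage and RPLS. Section 9.4 gives cabozantinib one dose reduction before it must stop. Section 9.5 allows a 4-week hold for cabozantinib and 12 weeks for pembrolizumab. In Table 9.5.3.1, the row for bleeding suggestive of portal hypertension stops cabozantinib and lets pembrolizumab restart. The rows for ALT/AST above 20 × ULN and Child-Pugh above 8 do the same. However, Section 12.0 ends study treatment for ALT above 20 × ULN or Child-Pugh above 8 when the event is not reversible and manageable, and footnote 2 of the table may allow cabozantinib back in the Child-Pugh case.

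**Does the protocol attach a period to pembrolizumab?** Section 8.4 advises against liver transplantation for at least 120 days after pembrolizumab and equates this with 5 half-lives, or 120 / 5 = 24 days each. Section 1.4.1.3 gives cabozantinib a terminal half-life of 99 hours, or 99 / 24 = 4.1 days, in renal cell carcinoma. The transplant advice concerns a different risk and does not set a contraception period. It does show that the clause is tied to the drug that clears faster.

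**The case against.** The strongest reply is that little is left uncovered. Section 12.0 already shows the intended contraception window, and a patient who follows the longest rule satisfies them all. This is therefore a mismatch of starting points and not a contradiction. The synopsis lists the follow-up period under study duration, so the course of the study may well include it, and the gap would then mostly close. The documents do not say that a sperm-donation ban is needed after pembrolizumab, so the cabozantinib anchor for that rule could be deliberate. The consent wording is not available here.

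Most of this stands and keeps the point minor. It does not remove it. Section 12.0 is a reason to stop treatment, so it can act on a refusal voiced during treatment but not after treatment has ended. It also does not mention sperm donation. The protocol gives no reason for the narrower anchor, and a patient should not have to work out where the course of the study ends.

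Two stronger readings are tempting, and the documents do not support them.

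- A reader might infer that contraception and the donation ban lapse while pembrolizumab is still being given alone. They do not: both apply throughout the course of the study as well as in the tail.
- A reader might infer that Section 12.0 conflicts with Appendix 8, because it refers to "Sexually active subjects who refuse to use medically accepted barrier methods of contraception (Appendix 8) during the course of the study" and none of the eight entries available in that appendix is a barrier method. The contents list places Appendix 8 at page 96 and the references at page 100, so missing text cannot be excluded. That reading is unverified and forms no part of this point.

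**Conclusion.** Inclusion 13 is wrong as written in one respect: its tail starts from the last dose of one drug, while the protocol's other windows start from the end of all treatment. The severity is low. The shortfall against Section 12.0 is min(120, 30g) days if the course of the study ends at the last dose. For g of 4 or more it is 83 to 90 days if that course ends at the discontinuation visit. It is nil if both drugs stop together, or if the course of the study runs far enough into follow-up. These figures rest on 30-day months and an assumed g, and the documents do not allow a count of patients concerned. The two-stage design, its error rates and the primary analysis are unaffected.

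**What to change.** In inclusion 13, in both the synopsis and Section 5.1, replace the end of the clause with: *for at least 4 months after the last dose of cabozantinib or pembrolizumab, whichever is later*. Keep the sperm-donation sentence on that same period. Check that the consent form says the same. Section 16.4.2 already uses the whichever-is-later form for adverse events, so no new concept is introduced.

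The cost is one phrase in two places and a matching consent line. Sample size, visits and analysis do not change.
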